6.2.1. Supply, Packaging and Labelling

AZD4547 will be packaged, labelled and distributed to sites by Fisher Clinical Services. Labels will be prepared in accordance with Good Manufacturing Practice Annex 13 requirements and local regulatory guidelines.

AZD4547 will only be dispatched to sites after receipt of confirmation that the regulatory checklist is complete.

6.2.2. Storage and Dispensing

The investigational products must be stored in a secure area with access limited to the Investigator and authorised site staff. AZD4547 film-coated tablets should be stored below 30°C in the original pack until use. Maintenance of a temperature log (manual or automated) is required. For further information investigators should refer to the investigator brochure.

The investigational product should only be dispensed and administered as directed in the protocol, and only by site staff authorised to do so i.e. pharmacist / trials technician. Only subjects enrolled in the trial may receive investigational product. AZD4547 will be dispensed at the beginning of each cycle of combination treatment.

6.2.3. Dosage and Duration

AZD4547 will be administered orally twice daily in a tablet formulation. A cycle of treatment will be defined as 28 days: one week of AZD4547 twice daily in combination with either anastrozole or letrozole once daily, followed by one week of either anastrozole or letrozole once daily alone, and the intermittent schedule repeated once more to complete one cycle.

For procedures relating to dose modification, dosing interruption and restarting of AZD4547 for subjects in both the safety run-in and phase IIa study, see 6.2.8.

6.2.3.1. Safety run-in

Dosing will begin with AZD4547 at 80 mg, twice daily given on an intermittent schedule of one week on/one week off.

Patients will be enrolled to ensure a minimum of 3 and a maximum of 6 evaluable patients per cohort. Dose de-escalation will occur according to the following conditions:

If one patient experiences a DLT in a group of 3 or more evaluable patients, then the cohort will be expanded to include 6 evaluable patients. If no more than one DLT is observed in the complete cohort of 6 evaluable patients then, with SRC review, this dose will be taken forward for the phase IIa part of the study.

If 2 or more patients experience a DLT in a group of up to 6 patients, irrespective of the number of patients enrolled, the combination dose will be considered not tolerated and recruitment to the cohort will cease. Instead, a lower intermediary combination dose (de-escalation) may be considered in order to better define the combination MTD.

There will be no intra-patient dose escalations.

The dose for subsequent cohorts or a decision to stop recruitment to the safety run-in part of the study will be agreed by the Safety Review Committee (SRC) after review of the data from each cohort. A different dose level of AZD4547 may be selected for combination with anastrozole than letrozole.

6.2.3.2. Phase IIa

The dose of AZD4547 to be used in combination with anastrozole and letrozole in the phase IIa part of the study has been determined in the safety run-in, i.e. 80 mg, twice daily given on an intermittent schedule of one week on/one week off.

N.B. If 2 or more cases of severe toxicity (leading to permanent discontinuation of study drug) are observed in the first 6 patients, an alternative schedule of two weeks on / one week off will be considered, if emerging data from other AZD4547 studies suggest that this is a better tolerated schedule. A cycle of treatment will be defined as 28 days: e.g. Cycle 1, two weeks of AZD4547 twice daily in combination with either anastrozole or letrozole once daily, followed by one week of either anastrozole or letrozole once daily alone, then one week of AZD4547 twice daily in combination with either anastrozole or letrozole once daily to complete the cycle.

6.2.4. Definition of Dose-Limiting Toxicity for assessment of safety and tolerability of AZD4547 in the safety run-in study

A DLT is defined as any toxicity not attributable to the disease or disease-related processes under investigation, which occurs after the first dose of AZD4547 at start of cycle 1 and before the end of cycle 1 (the DLT assessment window) and includes:

1. Haematological toxicity = CTCAE grade 4 present for more than 4 days
2. Non-haematological toxicity \geq CTCAE grade 3 including:
 - Infection including febrile neutropenia (Grade 3 with temperature $\geq 38.5^{\circ}\text{C}$ or Grade 4 with temperature $\geq 38^{\circ}\text{C}$)
 - QTc prolongation (> 500 msec) or QTc increase > 60 msec from baseline

3. Any other toxicity that is greater than that at baseline, is clinically significant and/or unacceptable, does not respond to supportive care and results in a disruption of dosing schedule of more than 14 days
4. Any event, including significant dose reductions or omissions, judged to be a DLT by the SRC

A DLT excludes:

1. Alopecia of any grade
2. Isolated laboratory changes of any grade without clinical sequelae or clinical significance

6.2.5. Definition of Severe Toxicity for Assessment of Safety and Tolerability of AZD4547 in the PIIa study

For the purposes of the PIIa study, severe toxicity is defined as indicated above (6.2.4), but occurring after the first dose of AZD4547 at start of cycle 1 until study treatment discontinuation.

6.2.6. Definition of Evaluable Patient

6.2.6.1. Safety run-in

The safety run-in analysis set (SRIS) will be used for decisions on dose de-escalation and definition of dose to take forward into the phase IIa part of the study. The SRIS includes any patient that has received AZD4547 and either:

has completed minimum safety evaluation requirements and has received at least 80% of the specified dose (both AZD4547 and anastrozole / letrozole) during the first 28 day cycle

or

has experienced a DLT during the first 28 day cycle

In the safety run-in, patients that are withdrawn from the study but are deemed evaluable will not be replaced. Any patient that is withdrawn and not evaluable will be replaced to ensure the minimum number of evaluable patients is achieved.

6.2.6.2. Phase IIa

The intention-to-treat analysis set (ITTS) will be used for the efficacy analysis. The ITTS includes all study patients irrespective of drug compliance to study medication.

6.2.7. Safety Review Committee

In the safety run-in, once there are at least 3 evaluable patients at a dose level the SRC will review and assess all available safety data from the cohort together with available PK and pharmacodynamic data to make a decision on the dose for the next cohort of patients. Any dose interruptions and reductions will be taken into account. If there are still other patients that are ongoing at the time of the review, the SRC may decide to defer their decision until these further patients become evaluable.

6.2.8. Dose Modifications for AZD4547

If a patient experiences a clinically significant and/or unacceptable toxicity including a DLT not attributable to the disease or disease-related processes under investigation, where the Investigator considers the AE of concern to be specifically associated with AZD4547, dosing with AZD4547 will

be interrupted or the dose reduced and supportive therapy administered as required (see Figure 4 and Table 6).

If the toxicity resolves or reverts to a clinically acceptable level (at least \leq CTCAE grade 2) within 14 days of onset and the patient is showing clinical benefit, study medication may be restarted using the rules below for dose modifications (see Figure 4) and with discussion and agreement with the Sponsor Study Team as needed.

If the toxicity does not resolve to a clinically acceptable level (at least \leq CTCAE grade 2) after 14 days, then the patient should have study medication permanently discontinued and observed until resolution of the toxicity.

If a patient experiences a doubling of phosphate from baseline or a corrected calcium:phosphate product $> 4.5\text{mmol/L}$ then the patient may remain on study treatment but phosphate chelation therapy (non-calcium containing agent) must be initiated, and clinical chemistry monitored weekly until resolution of the parameter to below the intervention limit. Investigators must seek appropriate specialist medical consultation (renal or metabolic) to advise on the prescription and titration of phosphate chelation agents, and to raise the patients awareness of low phosphate diets.

If patients experience toxicities regarding the anterior aspect of the eye (dry eyes, punctate keratopathy and keratitis) such events must be clinically managed to prevent secondary consequences e.g. secondary infections following corneal abrasions. Lubricating eye drops/replacement tears should be used; if there is any indication of extra eyelash growth or eyelashes rubbing on the cornea then these eyelashes should be removed. It is anticipated that patients will report any visual disturbances or discomfort relating to the eye in advance of any significant pathology such as ulceration occurring. The decision to continue on study treatment if mild corneal changes in the eye examination are observed will be left to the Investigator's discretion, since a patient may indicate a wish to tolerate minor discomfort if there is perceived clinical benefit from the therapy. A patient should also be permanently discontinued from AZD4547 if corneal ulceration occurs, and appropriate expert ophthalmologic consultation should be initiated.

RPED has been identified in clinical studies with AZD4547 (45 occurrences as of 04 June 2014).

The prognosis is generally good if there is no actual haemorrhage from the capillaries and no evidence of any fibrovascular growth in the sub-RPE space.

An ophthalmological assessment is required if there are any of the following at any time:

- Abnormalities in the Amsler grid test
- Changes in near vision acuity
- Blurred vision
- Distortion of central vision

Subsequent management should be according to the algorithm included in Figure 5 and Figure 6. Any patients with an optical coherence tomography (OCT) scan diagnostic of RPED should be managed according to the same algorithm.

Table 6: Dose Interventions

Starting Dose	X mg bd
Reduced dose -1	X/2 mg bd
Reduced dose -2	(Reduced dose -1)/2 mg bd

Figure 4: AZD4547 Dose Modifications for Toxicity

[figure not shown]
[figure not shown]

[figure not shown]
Figure 5: Management guidelines for patients with visual symptoms of ocular toxicity

a: After permanent discontinuation of AZD4547 due to ocular toxicity, patients should be managed according to local clinical practice

b: Only 1 dose reduction allowed for management of RPED or SRF.

MedDRA Medical Dictionary for Regulatory Activities; OCT Optical-coherence-tomography; RPED or SRF This grouped term includes RPED (MedDRA preferred terms of detachment of retinal pigment epithelium and detachment of macular retinal pigment epithelium), MedDRA preferred term subretinal fluid, MedDRA preferred term serous detachment, MedDRA preferred term retinal detachment (MedDRA lower level term: serous retinal detachment); SRF Subretinal fluid

Figure 6: Toxicity management guidelines for patients with no visual symptoms of ocular toxicity

a: Progression of RPED or SRF is defined as development of visual symptoms, extension from para-macular to macula, or increase in the number of lesions.

b: Only 1 dose reduction allowed for management of RPED or SRF.

c: After permanent discontinuation of AZD4547 due to ocular toxicity, patients should be managed according to local clinical practice.

MedDRA Medical Dictionary for Regulatory Activities; OCT Optical-coherence-tomography; RPED or SRF This grouped term includes RPED (MedDRA preferred terms of detachment of retinal pigment epithelium and detachment of macular retinal pigment epithelium), MedDRA preferred term subretinal fluid, MedDRA preferred term serous detachment, MedDRA preferred term retinal detachment (MedDRA lower level term: serous retinal detachment); SRF Subretinal fluid.

6.2.9. Accountability

Patients should return all unused study medication and empty packaging to the Investigator.

A drug accountability record of the number of tablets dispensed to and returned by each subject will be maintained by the study pharmacist. This form is not part of the CRF but is maintained in the study TMF.

In accordance with local regulatory requirements, the investigator / designated site staff will document the amount of study drug received from Fisher Clinical Services, the amount (with date) dispensed to study subjects, the amount (with date) returned by study subjects and the amount destroyed locally.

Product accountability records will be maintained throughout the course of the study and filed with delivery documentation. Destruction will be documented as per local policy.

6.2.10. Compliance

The compliance of the patient will be assessed at each visit using the patient diary and the accuracy of the patient diaries will be cross checked with drug accountability records. At each visit, the cause of any missed doses should be discussed. Any AE(s) associated with missed doses must be recorded in the CRF. Subjects should be instructed on the importance of compliance to study treatments.

6.2.11. Drug Interactions/Precautions

6.2.11.1. Restrictions

The following restrictions apply while the patient is receiving study treatment and for the specified times before and after:

1. All patients should avoid concomitant use of drugs, herbal supplements and/or ingestion of foods known to modulate CYP3A4 or CYP2D6 enzyme activity and drugs that are known to be CYP3A4 substrates from the time they enter the screening period until 2 weeks after the last dose of study treatment. Please refer to Appendix B for further details.
2. Patients must not use oestrogen-containing agents such as hormone replacement therapy.
3. Patients with uncontrolled glaucoma or intra-ocular pressure ≥ 21 mm Hg at screening should be referred for ophthalmological management and the condition controlled prior to first dose.

6.2.11.2. Concomitant Treatments

Information on any treatment in the 4 weeks prior to starting study treatment and all concomitant treatments given during the study, with reasons for the treatment, will be recorded in the CRF. If medically feasible, patients taking regular medication, with the exception of potent inhibitors or inducers of CYP3A4 or CYP2D6 or substrates of CYP3A4, should be maintained on it throughout the study period.

Patients should not be administered calcium-containing phosphate chelation agents, such as calcium acetate, for the management of hyperphosphataemia whilst receiving study treatment due to the increased risk of precipitating ectopic tissue mineralisation.

Other anticancer agents, investigational agents and radiotherapy should not be given while the patient is on study treatment although radiation for palliation at focal sites is permitted.

Patients may receive treatment with corticosteroids and/or bisphosphonates for the treatment of bone metastases.

Patients may take warfarin or a coumarin preparation but it is recommended that they should have their anticoagulation monitored carefully and dose adjusted accordingly.

Supportive care and other medications that are considered necessary for the patient's well-being may be given at the discretion of the Investigator.

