4.2.2. Exclusion Criteria

1. Treatment with any of the following:
 - a. **Safety run-in:** more than 1 regimen of endocrine therapy for advanced breast cancer
 - b. previous exposure to any FGFR inhibitor
 - c. **Safety run in:** more than 1 prior regimen of chemotherapy for advanced breast cancer.
 - d. potent inhibitors or inducers of CYP3A4 or CYP2D6, or substrates of CYP3A4 within 2 weeks prior to first dose of study treatment (3 weeks for St John's Wort)
 - e. major surgery within 4 weeks prior to first dose of study treatment
 - f. radiotherapy with a wide field of radiation within 4 weeks prior to first dose of study treatment; or radiotherapy with a limited field of radiation for palliation within 2 weeks before the first dose of study treatment
2. With the exception of alopecia, any unresolved toxicities from prior therapy greater than CTCAE grade 1 at time of starting study
3. Spinal cord compression or brain metastases unless asymptomatic, treated and stable and not requiring steroids for at least 4 weeks prior to start of study treatment
4. Any evidence of severe or uncontrolled systemic diseases or active infection
5. Any of the following cardiac criteria:
 - a. Resting corrected QT interval (QTc) >470 ms
 - b. Any clinically important abnormalities in rhythm, conduction or morphology of resting ECG e.g. complete left bundle branch block, third degree heart block
 - c. Any factors that increase the risk of QTc prolongation or risk of arrhythmic events such as heart failure, hypokalaemia, congenital long QT syndrome, family history of long QT syndrome or unexplained sudden death under 40 years of age or any concomitant medication known to prolong the QT interval
6. Inadequate bone marrow reserve or organ function as defined by any one of the following parameters:

Haemoglobin < 9.0 g/dL (<90.0 g/L)
Absolute neutrophil count (ANC) < 1.5×10^9 /L
Platelet count < 100×10^9 /L
Alanine aminotransferase > 2.5 x ULN if no demonstrable liver metastases or > 5 x ULN in the presence of liver metastases
Aspartate aminotransferase > 2.5 x ULN if no demonstrable liver metastases or > 5 x ULN in the presence of liver metastases
Total bilirubin > 1.5 x ULN if no demonstrable liver metastases or > 3 x ULN in the presence of liver metastases
Creatinine > 1.5 times ULN or creatinine clearance <50ml/min
Corrected calcium > ULN
Phosphate > ULN

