Treatment dosing		Treatment will be administered according to details in Section 6.2.3.										
Adverse events	X ⁸	X	X	X	X	X	X	X	X	X	X	X
Paired tumour biopsy (optional)	X ⁹				X ¹⁰							
Pharmacogenetics sample (optional)		X										
Circulating tumour specific DNA (ctDNA) (optional)	X ¹¹	X	X	X	X	X	X	X	X	X	X	X

¹ Either anastrozole or letrozole

² If an archival sample is not available, a fresh tumour biopsy sample must be taken.

³ **ONLY** radiation for palliation at focal sites is permitted whilst the patient is on study medication

⁴ After the cycle 3, day 1 assessment, MUGA/ECHO should be performed every three months i.e. at the end of cycles 5, 8 etc. and at discontinuation of AZD4547.

⁵ After first 3 months of AZD4547, ophthalmological review should be every 8 weeks (+/- 1 week) i.e. at the end of cycles 5, 7 etc. and at discontinuation of AZD4547

⁶ Tumour assessments to be carried out at baseline, week 6, week 12, then every 8 weeks until disease progression or permanent discontinuation of study treatment and finally at AZD4547 discontinuation visit.

⁷ If a patient has AZD4547 treatment delays, please contact the Study Team for advice regarding appropriate timing of PD biomarker assessments

⁸ AEs collected from the point the patient has been confirmed to be eligible by the RADICAL study team

⁹ The first biopsy must only be taken once the patient has been confirmed to be eligible by the RADICAL study team.

¹⁰ The second biopsy **must be taken within 18 hours** of administration of previous AZD4547 dose

¹¹ Sample to be taken within 1 week of Cycle 1 day 1

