5.2.3. Previous and Current Radiotherapy

Radiotherapy includes all treatments prior to study entry, whilst on the study, or post permanent discontinuation of study treatment. The following will be collected: site or region (breast, local lymph nodes, distant lymph nodes, bone, brain, or other), setting (neoadjuvant; adjuvant; metastatic), range of field given (wide or limited) and start and end dates of treatment.

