5.2.21. Tumour Assessments (Phase IIa only)

Tumour assessments will be performed using CT or MRI scans of the chest, abdomen and pelvis. The same method used for assessment at baseline must be used at all subsequent time points.

Tumour assessment will include: if disease is measurable or non-measurable (at least one lesion must be measurable), date of assessment, imaging method used, site (breast, lung, liver, pleural effusion, local lymph nodes, distant lymph nodes, bone, brain or other site), longest diameter of each target lesion and sum of longest diameters for all target lesions.

Patient response to treatment will be assessed using RECIST v1.1 criteria. Tumour size, Progression Free Survival and Objective Response Rate will all be determined.

Tumour Size, will be assessed at baseline and on scans at subsequent time points and recorded as the sum of the longest diameters of the target lesions.

Progression Free Survival (PFS) is defined by the progression criteria of RECIST.

Objective Response Rate (ORR) is defined as the percentage of patients who have at least one visit response of CR or PR prior to any evidence of progression (as defined by RECIST v1.1)

The RECIST v1.1 (January 2009) guidelines for measurable, non-measurable, target and non-target lesions and the objective tumour response criteria (complete response, partial response, stable disease or progression of disease) are detailed in Appendix A

Baseline assessment should be performed no more than 28 days before the start of study treatment and ideally as close as possible to the start of study treatment; it should include all areas known for possible breast cancer metastases.

Subsequent tumour assessments will be conducted at week 6, week 12 (primary endpoint) and then every 8 weeks until objective disease progression or cessation of study treatment and finally at AZD4547 discontinuation visit. The window for each assessment is ± 1 week.

Duplicates will be made of all CT/MRI scans. These duplicate scans will be collected to enable an independent review of progression.

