13. APPENDICES

Appendix A: Guidelines for Evaluation of Objective Tumour Response Using RECIST 1.1 (Response Evaluation Criteria in Solid Tumours)

(ICTU-Cancer guidance document v2.0 dated 17 November 2014)

Response and progression will be evaluated in this study using the new international criteria proposed by the revised Response Evaluation Criteria in Solid Tumours (RECIST) guideline (version 1.1) [*Eur J Ca* 45:228-247, 2009]. Changes in the largest diameter (unidimensional measurement) of the tumour lesions and the shortest diameter in the case of malignant lymph nodes are used in the RECIST criteria.

Definition of Disease Parameters

Measurable disease Must be accurately measured in a least one dimension (longest diameter in the plane of measurement is to be recorded) with a minimum size of:

- 10mm by CT scan (CT scan slice thickness no greater than 5mm; when CT scans have slice thickness >5mm, the minimum size should be twice the slice thickness).
- 10mm caliper measurement by clinical exam (lesions which cannot be accurately measured with calipers should be recorded as non-measurable).
- 20mm by chest X-ray.

Note: Tumour lesions situated in a previously irradiated area or in an area subjected to other loco-regional therapy are usually not considered measurable unless there has been demonstrated progression in the lesion. Study protocols should detail the conditions under which such lesions would be considered measurable.

Malignant lymph nodes Criteria for lymph nodes given as ≥ 15 mm short axis for target lesions and 10mm to <15mm for non-target lesions. Nodes under 10mm to be considered non-pathological.

Non-measurable disease All other lesions, including small lesions (longest diameter <10 mm or pathological lymph nodes with 10 to <15 mm short axis), as well as truly non-measurable lesions. Lesions considered truly non-measurable include; leptomeningeal disease, ascites, pleural/pericardial effusions, inflammatory breast disease, lymphangitic involvement of skin or lung, abdominal masses/abdominal organomegaly identified by physical exam that is not measurable by reproducible imaging techniques.

Note: Lytic bone lesions or mixed lytic-blastic lesions with identifiable soft tissue components that can be evaluated by cross-sectional imaging techniques such as CT or MRI can be considered measurable if the soft tissue component meets the definition of measurability described above.

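### A target lesion irradiated for palliation during study treatment stays in the tumour sum, so radiation shrinkage counts as treatment effect in the week 12 primary endpoint

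*Protocol*

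**What the plan says.** **On treatment.** Section 6.2.11.2 states that "radiotherapy should not be given while the patient is on study treatment although radiation for palliation at focal sites is permitted". Footnote 3 of Table 2 (Phase IIa study plan, section 5.1) repeats that "radiation for palliation at focal sites is permitted whilst the patient is on study medication". Neither separates target from non-target lesions.

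**The endpoint.** Under 5.2.21, tumour size is "recorded as the sum of the longest diameters of the target lesions", with no exception for an irradiated lesion. Under 8.2.6 a patient is evaluable with a week 12 scan (within a week either side) or earlier progression, and 8.2.7 assesses the endpoint in all patients. Neither mentions radiotherapy.

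**Before the first dose.** Exclusion criterion 1f bars "radiotherapy with a wide field of radiation within 4 weeks prior to first dose of study treatment", and "radiotherapy with a limited field of radiation for palliation within 2 weeks before the first dose of study treatment". Section 5.2.21 says "Baseline assessment should be performed no more than 28 days before the start of study treatment", and ideally as close to that start as possible.

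**Appendix A.** Lesions in a previously irradiated area are usually not measurable unless they have since progressed. The appendix adds: "Study protocols should detail the conditions under which such lesions would be considered measurable". Inclusion criterion 8 and section 5.2.21 give no such conditions.

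**Data collected.** Section 5.2.3 records radiotherapy by broad anatomical region, with setting, field range and dates. It does not record whether a target lesion was in the field.

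**The concern.** Focal radiotherapy is a local treatment that can act directly on the quantity the trial measures. In a randomised trial some of that effect would appear in both arms. Here there is one arm, so any radiation shrinkage of a target lesion is read as an effect of AZD4547 plus the aromatase inhibitor. The expected direction favours the study treatment.

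Overlap between irradiated and target lesions is plausible. Criterion 8 requires only one measurable lesion and admits bone-only disease with a lytic or mixed lesion, and bone is one of the radiotherapy sites listed in 5.2.3. In such a patient the irradiated lesion may be the whole sum.

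The effect would also reach RECIST response, the objective response rate, the waterfall plot, progression-free survival and the interim rule, which continues the study if at least 4 of 20 patients show clinical benefit. Stable disease counts as benefit there, so holding one lesion below the progression threshold can be enough.

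**Working it through.** **1. The plan's own precision.** Inputs from section 8.1: N = 50, SD 0.30 for change in log tumour size, two-sided 95% interval.

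- Half-width = 1.96 × 0.30 / √50 = 0.0832, and exp(0.0832) = 1.087.
- With the t distribution on 49 degrees of freedom: 0.0853, and exp(0.0853) = 1.089.

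The stated 0.083 and 1.09 reproduce.

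**2. Shift in the primary endpoint.** Let f be the share of patients with a target lesion irradiated after baseline, and s the extra proportional fall in their tumour sum. The mean log change shifts by f × ln(1 − s). The documents give neither f nor s; the ranges below are assumptions.

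| f | s | shift in mean log change | factor on geometric mean ratio | share of half-width |
|---|---|---|---|---|
| 5% | 10% | −0.0053 | 0.995 | 6% |
| 10% | 20% | −0.0223 | 0.978 | 27% |
| 20% | 30% | −0.0713 | 0.931 | 86% |

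A shift equal to the full half-width would need f = 0.0832 / 0.357 = 23% at s = 30%, or 0.0832 / 0.223 = 37% at s = 20%.

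**3. The interim count.** Section 8.2.1 sets 5% as the uninteresting rate, 30% as the rate of interest, one-sided type I error 0.05 and power 85%.

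- As planned: P(at least 4 of 20) is 0.016 at a true rate of 5% and 0.893 at 30%. Both stated limits are met.
- If radiotherapy turns exactly one true failure into stable disease, 3 genuine benefits pass as 4: P(at least 3 of 20 at 5%) = 0.075, above 0.05.
- If instead each patient's chance of being scored as benefit rises from 5% to 7.5%, the probability of passing is 0.058; at 10% it is 0.133.

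These are illustrations, because the frequency is unknown.

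**4. The gap before the first dose.** The baseline scan may be up to 28 days old, and limited-field radiotherapy is barred in the last 14 days. The gap is at most 28 − 14 = 14 days, and exists only if the scan is more than 14 days before the first dose. Wide-field radiotherapy is barred for 4 weeks, which matches the scan window and leaves essentially no gap.

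**5. Does Appendix A close the on-treatment route?** Its note concerns whether a lesion is measurable, and so whether it can be chosen as a target. It covers lesions irradiated before selection and arguably those irradiated before the first dose. It does not say what happens to a target lesion, validly chosen at baseline, that is irradiated later. The response tables in Appendix A do not say either.

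**The case against.** A reader might infer that nothing in the protocol keeps irradiated lesions out of the sum. The documents do not support that: Appendix A is part of the protocol and its default makes previously irradiated lesions usually non-measurable.

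A reader might also take the whole screening window to be open. It is not. The route needs an older scan and a limited-field course to a target lesion within about two weeks, against advice to scan close to the start of treatment.

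A third tempting reading is that patients who are failing will generally be rescued by radiotherapy. New lesions, unequivocal non-target progression and target growth that already meets the criterion remain progression under Appendix A. Only patients irradiated before meeting those criteria, and without progression elsewhere, are affected.

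Traceability is better than section 5.2.3 alone suggests: radiotherapy dates, lesion sites and duplicate scans are collected, so many affected lesions could be found. With several lesions in one region, some might not be.

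The strongest objection is that handling of measurements after another therapy is commonly left to the SAP, which is not at hand. That would answer a mere silence. Here, however, the protocol states a measurement rule that, followed as written, yields a biased value. The choice of target lesions and the form fields must be settled before data are collected. Section 8.2.2 requires the SAP only before the preliminary final analysis, so the interim decision can come first.

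**Conclusion.** The on-treatment gap is real and sufficient by itself. Focal palliative radiation is allowed without regard to target lesions, and the tumour-size and evaluability rules make no provision for it. The pre-dose gap is smaller, and Appendix A arguably covers part of it.

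The size cannot be derived from the documents. Under the assumed 5% to 20% of patients and 10% to 30% extra fall, the bias is about 6% to 86% of the 0.083 half-width, and 27% at 10% and 20%. It would be minor if such radiotherapy is rare and material if it is common. A reader might infer that it invalidates the primary result; the documents do not support that. The primary analysis is an interval with no pass or fail threshold, and neither N = 50 nor the half-width calculation changes. The interim rule has less room: one misclassified patient is enough to take its false-continuation probability above the stated 0.05.

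**What to change.** Make these changes as measurement rules only, leaving access to palliation unchanged.

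- **5.2.21:** state that measurements of a target lesion taken after it is irradiated are not used as drug effect. Drop that lesion from both the baseline and the follow-up sums.
- **8.2.6 and 8.2.1:** if no other target lesion remains, the patient is non-evaluable for tumour size unless progression was already shown, and is not counted as response or clinical benefit on the basis of post-radiotherapy scans.
- **Sensitivity analysis:** count these patients as progressed at the date of radiotherapy. This is needed because leaving them out may itself remove patients who are doing badly.
- **Between baseline scan and first dose:** if a measured lesion is irradiated, use another target lesion or a repeat baseline measurement.
- **5.2.3:** add a field recording whether a target lesion was in the radiation field.

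Carrying the last pre-radiotherapy sum forward to week 12 is a weaker choice. For a patient irradiated before the week 6 scan that sum is normally the baseline, so the change is scored as zero. It also sits badly with section 8.2.4, which rules out imputation of missing primary-endpoint data in the primary analysis.

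The cost is a few sentences and one form field. A few patients will contribute a less favourable value, or none.
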